11.2 Breaking of blinded codes

If the trial site needs to break the code, Novo Nordisk should, if possible, be contacted before the code is broken. The IV/WRS will notify Novo Nordisk (monitor and the Global Safety department) immediately after the code is broken.

The code for a particular subject may be broken in a medical emergency if knowing the actual treatment would influence the treatment of the subject. Whenever a code is broken the person breaking the code must print the Code Break Confirmation Notification generated by the IV/WRS, record the reason, and sign and date the document.

If the subject is withdrawn after the code has been broken, a withdrawal session should be completed in the IV/WRS.

When the code is broken, the treatment allocation will be accessible to the investigator and the Novo Nordisk Global Safety department, and any other relevant party. If the IV/WRS is not accessible at the time of code break the IV/WRS vendor helpdesk should be contacted. Contact details are listed in attachment II.

Key codes will be disclosed to the sponsor after the 1st database lock in this trial to analyse and submit the data from the pivotal phase to the Authority. Even after the key open, investigators, sub-investigators and the subjects will be kept blinded until the 2nd database lock.

12 Adverse events, and technical complaints

12.1 Definitions

An **adverse event** (AE) is any untoward medical occurrence in a subject administered a product, and which does not necessarily have a causal relationship with this treatment. An AE can therefore be any unfavourable and unintended sign (including an abnormal laboratory finding), symptom or disease temporally associated with the use of a product, whether or not considered related to the product.

AEs include:

- A clinically significant worsening of a concomitant illness.
- A clinical laboratory adverse event (CLAE): A clinical laboratory abnormality which is clinically significant, i.e., an abnormality that suggests a disease and/or organ toxicity and is of a severity that requires active management. Active management includes active treatment or further investigations, for example change of medicine dose or more frequent follow-up due to the abnormality.

The following should **not** be reported as AEs:

- Pre-existing conditions, including those found as a result of screening procedures (pre-existing conditions should be reported as medical history or concomitant illness).
- Pre-planned procedures unless the condition for which the procedure was planned has worsened from the first trial related activity after the subject's parent or subject's legally acceptable representative (and the subject in case the subject has the ability to understand) has signed the informed consent.

An AE is either a serious AE (SAE) or a non-serious AE.

An SAE is an experience that at any dose results in any of the following:

- Death
- A life-threatening ^{a)} experience
- In-patient hospitalisation ^{b)} or prolongation of existing hospitalisation
- A persistent or significant disability or incapacity ^{c)}
- A congenital anomaly or birth defect
- Important medical events ^{d)} that may not result in death, be life-threatening ^{a)} or require hospitalisation ^{b)} may be considered an SAE – when, based on appropriate medical judgement – they may jeopardise the subject and may require medical or surgical intervention to prevent one of the outcomes listed in this definition ^{d)}.
Suspicion of transmission of infectious agents must always be considered an SAE.

- a) The term “life-threatening” in the definition of SAE refers to an event in which the subject was at risk of death at the time of the event. It does not refer to an event which hypothetically might have caused death if it was more severe.
- b) The term “hospitalisation” is used when a subject:
- is admitted to a hospital or in-patient, irrespective of the duration of physical stay, or
 - stays at the hospital for treatment or observation for more than 24 hours.
- Medical judgement must always be exercised, and when in doubt, the hospital contact should be regarded as a hospitalisation. Hospitalisations for administrative, trial related and social purposes do not constitute AEs and should therefore not be reported as AEs or SAEs. Hospital admissions for surgical procedures, planned before trial inclusion, are not considered AEs.
- c) A substantial disruption of a subject’s ability to conduct normal life functions (e.g., following the event or clinical investigation the subject has significant, persistent or permanent change, impairment, damage or disruption in his/her body function or structure, physical activity and/or quality of life).
- d) For example intensive treatment in an emergency room or at home of allergic bronchospasm, blood dyscrasias or convulsions that do not result in hospitalisation, or development of drug dependency or drug abuse.

A **non-serious AE** is any AE which does not fulfil the definition of an SAE.

In addition to being either an SAE or non-serious AE, some AEs fulfil the below medical event of special interest criteria which must be evaluated by the investigator for each adverse event.

A **medical event of special interest (MESI)** is an event which, in the evaluation of safety, has a special focus.

The following are defined as MESIs in this trial:

Table 12-1 List of MESIs

MESIs	Definitions
Medication errors concerning trial products	The following should be reported: 
• Administration of wrong drug• Wrong route of administration, such as intramuscular instead of subcutaneous• Administration of a high dose with the intention to cause harm (e.g., suicide attempt)• Administration of an accidental overdose, i.e., a dose which may lead to significant health consequences, as judged by the investigator, irrespective of whether the SAE criterion is fulfilled

Severity assessment definitions:

- **Mild** – No or transient symptoms, no interference with the subject’s daily activities
- **Moderate** – Marked symptoms, moderate interference with the subject’s daily activities
- **Severe** – Considerable interference with the subject’s daily activities, unacceptable.

The following terms and definitions are used in assessing the relationship between each AE and the relevant trial products:

- **Probable** – Good reasons and sufficient documentation to assume a causal relationship
- **Possible** – A causal relationship is conceivable and cannot be dismissed
- **Unlikely** – The event is most likely related to aetiology other than the trial product

The following terms and definitions are used in assessing the final outcome of an AE:

- **Recovered** – The subject fully recovered, or by medical or surgical treatment the condition has returned to the level observed at the first trial-related activity after the subject signed the informed consent
- **Recovering** – This term is only applicable if the subject has completed the trial or has died from another AE. The condition is improving and the subject is expected to recover from the event.
- **Recovered with sequelae** – The subject has recovered from the conditions, but with lasting effect due to disease, injury, treatment or procedure. If a sequela meets an SAE criterion, the AE must be reported as an SAE.
- **Not recovered** – The condition of the subject has not improved and the symptoms are unchanged, or the outcome is not known at the time of reporting.
- **Fatal** – This term is only applicable if the subject died from a condition related to the reported AE. Outcomes of other reported AEs in a subject before he/she died should be assessed as “recovered”, “recovering”, “recovered with sequelae” or “not recovered”. An AE with fatal outcome must be reported as an SAE.
- **Unknown** – This term is only applicable if the subject is lost to follow-up.

A **technical complaint** is any communication that alleges defects on trial supplies. The technical complaint may be associated with an AE, but does not concern the AE itself.

Examples of technical complaints:

- The physical or chemical appearance of trial products (e.g., discoloration, particles or contamination)
- The packaging material (e.g., leakage, cracks, rubber membrane issues or errors in labelling text)

- Problems related to devices (e.g., to the injection mechanism, dose setting mechanism, push button or interface between the pen and the needle)

12.2 Reporting of adverse events

All events meeting the definition of an AE must be collected and reported. This includes events from the first trial-related activity after the subject's parent or the subject's legally acceptable representative has signed the informed consent until the completion of procedures at Visit 20. The events must be recorded in the applicable forms in a timely manner.

During each visit, the subject and the subject's parent or the subject's legally acceptable representative must be asked about AEs and technical complaints in the following way: "Have you experienced any problems since the last contact?"

All AEs, either observed by the investigator or reported by the subject and the subject's parent or the subject's legally acceptable representative must be reported by the investigator and evaluated. Novo Nordisk' assessment of expectedness is performed according to the following reference documents:

- Current version of company core data sheet (CCDS/version 11.0/29 Feb 2012) and any updates hereof.

The investigator should report the diagnosis, if available. If no diagnosis is available, the investigator should record each sign and symptom as an individual AE.

All AEs must be recorded by the investigator on the AE form. A separate AE form should be used for each diagnosis or sign and symptom. For each SAE a safety information form should be completed in addition to the standard AE form. If several symptoms or diagnoses occur as part of the same clinical picture, one safety information form may be used to describe all the SAEs.

MESIs, regardless of seriousness, must be reported using both the AE form and the safety information form and a MESI form (the medication error form).

[figure not shown]

Figure 12-1 Reporting of adverse events

The investigator must ensure that the worst case severity and seriousness of an event is kept throughout the trial.

The investigator must complete and forward the following forms to Novo Nordisk either electronically (e.g., in PDF format) or by fax:

- If the AE fulfils the seriousness criteria: The AE form **within 24 hours** and the safety information form (SIF) **within 5 calendar days** of obtaining knowledge of the SAE.
- If a SAE fulfils the MESI criteria: The MESI form (the medication error form) **within 14 calendar days** of obtaining knowledge of the adverse event.

If a non-serious AE fulfils the MESI criteria: The AE form, SIF and MESI form (the medication error form) **within 14 calendar days** of obtaining knowledge of the adverse event.

Contact details (fax, telephone, e-mail and address) are provided in attachment I to the protocol.

Novo Nordisk will notify the investigator of trial product-related suspected unexpected serious adverse reactions (SUSARs) in accordance with the Japanese requirements and ICH GCP²⁵. In addition, the investigator will be informed of any trial-related SAEs that may warrant a change to any trial procedure.

Novo Nordisk must inform the institutional review boards (IRBs) in accordance with local requirement and GCP¹⁶, unless locally this is an obligation of the investigator, as for example in the US.

Novo Nordisk must always inform the regulatory authorities in accordance with the Japanese requirements and GCP¹⁶.

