8.5 Assessments for safety

8.5.1 Adverse events

AEs will be recorded at each visit in accordance with the procedures described in section [12.2](#). Any clinically significant worsening since baseline of a previous finding must be reported as an AE. For further information, please refer to section [12](#).

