12.3 Follow-up of adverse events

All SAEs must be followed up until the outcome of the event is “recovered”, “recovered with sequelae” or “fatal”, and until all queries have been resolved. Cases of chronic conditions, cancer or AEs ongoing at time of death (where death is due to another AE) may be closed with the outcome “recovering” or “not recovered”, when the subject has completed the follow up period.

The follow-up information should only include new (corrections or new or additional) information and should be reported **within 24 hours** of obtaining knowledge of the information. This is also the case for previously non-serious AEs which subsequently become SAEs.

Follow-up information on MESIs (not also fulfilling the SAE criteria) should only include new (corrections or new or additional) information and should be reported **within 14 calendar days** of obtaining knowledge of the information. This is also the case for previously non-serious AEs which subsequently fulfil the MESI criteria.

Non-serious AEs (not also fulfilling the MESI criteria) must be followed until the outcome of the event is “recovering”, “recovered” or “recovered with sequelae” or until the end of the follow-up period stated in the protocol, whichever comes first, and until all queries related to these AEs have been resolved. Cases of chronic conditions or cancer or AEs ongoing at time of death (where death is due to another AE) may be closed with the outcome “recovering” or “not recovered”.

Queries or follow-up requests from Novo Nordisk should be responded to within 14 calendar days.

The investigator must forward follow-up information on SAEs to Novo Nordisk within 24 hours of obtaining the follow-up information by using a new AE form and/or a safety information form marked as follow-up.

The investigator must forward follow-up information on MESIs (not fulfilling the SAE criteria) to Novo Nordisk within 14 calendar days of obtaining the follow-up information by using a new AE form and/or a safety information form and/or MESI form marked as follow-up.

The investigator must forward follow-up information on non-serious AEs (not fulfilling the MESI criteria) as corrections to the original AE form, or by using a new AE form marked as follow-up.

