17.4.2 Safety endpoints

Secondary safety endpoints during 104 weeks are as follows:

- Incidence of treatment emergent AEs during 104 weeks of treatment
- Change in IGF-I from baseline during 104 weeks of treatment
- Change in HbA_{1c} from baseline to 104 weeks of treatment
- Change in clinical laboratory tests from baseline during 104 weeks of treatment
- Change in glucose tolerance (AUC of glucose and AUC of insulin) based on the OGTT from baseline to 104 weeks of treatment
- Change in bone age and bone age/chronological age from baseline to 104 weeks of treatment, and (yearly [change in bone age] / [change in chronological age]) (yearly [Δ bone age/ Δ chronological age])
- Change in vital signs (blood pressures and pulse) from baseline during 104 weeks of treatment
- Change in urinalysis from baseline during 104 weeks of treatment
- Change in blood coagulation test from baseline during 104 weeks of treatment
- Change in ECG from baseline during 104 weeks of treatment

Incidence of treatment emergent adverse events during 104 weeks of treatment

AEs will be coded using the current version of the Medical Dictionary for Regulatory Activities (MedDRA). All AEs will be presented based on system organ class and preferred terms.

A treatment emergent adverse event (TEAE) is defined as an event that has onset date on or after the first day of exposure to NN-220 and no later than the date of Visit 12 (104 weeks). For withdrawal subjects, AEs with onset date no later than 7 days after the last day of NN-220 treatment will be included in the TEAE.

TEAEs are summarised descriptively, whereas non-treatment emergent AEs are presented in listings. TEAE data will be displayed in terms of the number of subjects with at least one event (N), the percentage of subjects with at least one event (%), the number of events (E) and the event rate per 100 years (R). Furthermore, TEAE data are summarised by seriousness, severity, relation to treatment, relation to device, withdrawal due to AEs and outcome.

Furthermore summary tables based on system organ class and preferred term are made for

- All TEAEs
- Serious TEAEs
- Possibly or probably related TEAEs
- Severe TEAEs
- Cardiac disease TEAEs
- TEAEs with preferred term that are experienced by at least 5% of the subjects in any treatment arm or by at least 5% of all subjects

IGF-I

IGF-I SDS will be derived using a reference range²⁹.

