2.4.2 Safety endpoints

Secondary safety endpoints during 104 weeks are as follows:

- Incidence of treatment emergent AEs during 104 weeks of treatment
- Change in IGF-I from baseline during 104 weeks of treatment
- Change in HbA_{1c} from baseline to 104 weeks of treatment
- Change in clinical laboratory tests from baseline during 104 weeks of treatment
- Change in glucose tolerance (AUC of glucose and AUC of insulin) based on the OGTT from baseline to 104 weeks of treatment
- Change in bone age and bone age/chronological age from baseline to 104 weeks of treatment, and (yearly [change in bone age] / [change in chronological age]) (yearly [Δ bone age/ Δ chronological age])
- Change in vital signs (blood pressures and pulse) from baseline during 104 weeks of treatment
- Change in urinalysis from baseline during 104 weeks of treatment
- Change in blood coagulation test from baseline during 104 weeks of treatment
- Change in ECG from baseline during 104 weeks of treatment

Incidence of treatment emergent adverse events during 104 weeks of treatment

AEs will be coded using the current version of the Medical Dictionary for Regulatory Activities (MedDRA). All AEs will be presented based on system organ class and preferred terms.

A treatment emergent adverse event (TEAE) is defined as an event that has onset date on or after the date of visit 2 (0 week) and no later than the date of Visit 12 (104 weeks). For withdrawal

subjects, AEs with onset date no later than 7 days after the last day of NN-220 treatment will be included in the TEAE.

TEAEs are summarised descriptively, whereas non-treatment emergent AEs are presented in listings. TEAE data will be displayed in terms of the number of subjects with at least one event (N), the percentage of subjects with at least one event (%), the number of events (E) and the event rate per 100 years (R). Furthermore, TEAE data are summarised by seriousness, severity, relation to treatment, relation to device, withdrawal due to AEs and outcome.

Furthermore summary tables based on system organ class and preferred term are made for

- All TEAEs
- Serious TEAEs
- Possibly or probably related TEAEs
- Severe TEAEs
- Cardiac disease TEAEs
- TEAEs with preferred term that are experienced by at least 5% of the subjects in any treatment arm or by at least 5% of all subjects
- Medication errors
 - HLGTS: Medication errors, Device issues and Product Quality Issue

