2.4.3 Endpoints for the whole trial including the extension phase

The period of the extension phase is 104 weeks, and the period of the whole trial will be 208 weeks [104 weeks in the pivotal phase and 104 weeks in the extension phase]. However, if the indication has not yet been approved or rejected by the PMDA at 208 weeks for the first subject, the period for the extension phase will be extended for at least 26 weeks (6 months).

The endpoints at 208 weeks for the whole trial including the extension phase are defined in the same way as for the pivotal phase.

All efficacy and safety endpoints and parameters will be summarised and analysed in the same way as for the 104 weeks.

TEAEs will be defined as an event that has onset date on or after the first day of exposure to NN-220 and no later than 7 days after the last day of NN-220 treatment.

3 Changes to the statistical analyses planned in the protocol

The following changes from the protocol are implemented in this SAP

Terminology

“Efficacy parameters” is changed to “secondary efficacy endpoints” in section 4.2 in the protocol version 2 but it is not reflected to the section 17. In this SAP, it is changed to “secondary efficacy endpoints” from “efficacy parameters”.

Exploratory analysis on the primary endpoint

In order to investigate effects of sex, age at start of treatment and baseline height SDS on the primary endpoint, change in height SDS from baseline to 104 weeks of treatment is analysed based on the ANCOVA model with treatment and sex as fixed effects and age at start of treatment and baseline height SDS as covariates.

Statistical analysis of height SDS according to the Noonan reference

A statistical analysis on change from height SDS according to the Noonan reference in the protocol is included.

Derivation of AUC

Imputation of missing data for each individual profile is specified.

Definition of treatment emergent adverse event

The date of visit 2 (0 week) instead of the first day of exposure to NN-220 is used for a definition of a treatment emergent adverse event since the first day of exposure to NN-220 is not available in the database by the end of treatment.

Treatment emergent adverse event based on pre-defined MedDRA search

Summary tables based on system organ class and preferred term are made for treatment emergent adverse event based on pre-defined MedDRA search.

4 References

-

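### TEAE status rests on onset date alone, so an AE that arises during screening and becomes serious, or worsens without a new record, on NN-220 is left out of the TEAE tables

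*Protocol*

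**What the plan says.** **Which events are treatment emergent.** For the 104-week analysis, SAP 2.4.2 counts "event that has onset date on or after the date of visit 2 (0 week"), up to Visit 12, or up to 7 days after the last dose for withdrawn children. Protocol 17.4.2 has the same structure but starts the clock at first exposure: "an event that has onset date on or after the first day of exposure to NN-220". For the whole trial, SAP 2.4.3 (like Protocol 17.4.3) says "TEAEs will be defined as an event that has onset date on or after the first day of exposure to NN-220", closing 7 days after the last dose. None of the four has a clause for an event that begins earlier and worsens on treatment.

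**What happens to the rest.** SAP 2.4.2: "TEAEs are summarised descriptively, whereas non-treatment emergent AEs are presented in listings".

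**How a change in an existing AE is recorded.** Protocol 12.2 collects AEs once trial activities begin after consent, so an AE can start before Visit 2. It adds: "The investigator must ensure that the worst case severity and seriousness of an event is kept throughout the trial". Protocol 12.3 sets the deadline for reporting follow-up information and continues: "This is also the case for previously non-serious AEs which subsequently become SAEs". Follow-up is entered by correcting the original form or by submitting a form marked as follow-up.

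**A rule that points the other way.** Protocol 8.5.1: "Any clinically significant worsening since baseline of a previous finding must be reported as an AE".

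**The concern.** Read together, these rules allow an AE record to be flagged serious or severe because of what happened on drug, yet be classed as not treatment emergent because it began in screening. It would then be absent from the tables of all, serious, severe and related TEAEs, and from the cardiac and MedDRA-search tables where it would otherwise qualify.

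TEAE incidence is the first-listed key secondary endpoint and safety is the only secondary objective (Protocol 1). The trial compares two doses, and aggravation on drug is part of what that comparison should show. For increases in severity there is a further problem. A site following 8.5.1 might open a new AE with an on-treatment onset, while a site following 12.2 and 12.3 updates the existing one. The same clinical course would then be a TEAE at one site and a listing entry at another.

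**Working it through.** The plan states no figure on this point, so the check is a reading of the rules followed by a bound on the numbers.

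**Tracing the cases**

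| Case | Rule that applies | Result |
|---|---|---|
| Condition present at Visit 1, or found by a screening procedure, worsens on drug | Protocol 8.2, 12.1; also 8.5.2 (laboratory), 8.5.3 (vital signs), 8.5.4 (ECG), 8.5.5 (TTE) | Not an AE at first; clinically significant worsening is reported as an AE and can carry an on-treatment onset. Can be a TEAE |
| AE arises in screening, then becomes serious on drug | Protocol 12.2, 12.3 | Follow-up of the existing event; onset stays before Visit 2. Listing only |
| AE arises in screening, then increases in severity on drug | 12.2 and 12.3 against 8.5.1 | Listing only if the record is updated; TEAE if a new record is opened. Not settled |
| Worsening amounts to a new diagnosis | Protocol 12.2 (separate form per diagnosis) | New record. TEAE |

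The gap is therefore the second row, and the third where no new record is made.

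**Bounding the numbers**

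Inputs from the documents: 48 children, 24 per arm (Protocol 6.1); at most 4 weeks from Visit 1 to Visit 2 (Protocol 8.1.4); 119 AEs in 179 treatment years in the Swedish trials (Protocol 3.1.1). The Swedish rate was observed on treatment and serves only as an illustration. Assumptions: a higher rate of 4 AEs per child-year, and 5% to 20% of screening AEs worsening on drug. The documents give neither.

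- Screening time, upper limit: 48 × 28 / 365.25 = 3.7 child-years.
- Time over 104 weeks: 48 × 728 / 365.25 = 95.7 child-years. Screening share: 4 / (4 + 104) = 3.7%.
- Swedish rate: 119 / 179 = 0.665 per year. Screening AEs: 3.68 × 0.665 = 2.4.
- At 4 per year: 3.68 × 4 = 14.7.
- Affected at the Swedish rate: 2.4 × 0.05 to 2.4 × 0.20 = 0.1 to 0.5 events.
- Affected at 4 per year: 14.7 × 0.05 to 14.7 × 0.20 = 0.7 to 2.9 events.

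**Weight of one child**

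1/24 = 4.2% and 2/24 = 8.3%. SAP 2.4.2 tabulates preferred terms reaching 5% in either arm or 5% overall. A term seen in two children in one arm and none in the other qualifies at 8.3%. If one of the two is missing, it falls to 4.2% of the arm and 1/48 = 2.1% overall, and drops out of that table.

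**The case against.** The strongest reply is that the documents contain many rules that bring worsening back in. Concomitant illness, laboratory results, vital signs, ECG and echocardiography each have one. The Visit 1 ECG, echocardiogram and OGTT may be done up to just before Visit 2 (Protocol 8.5.2.9; Amendment 3), and clinically significant ECG or echocardiographic findings then become concomitant illness rather than AEs. Cardiac and glucose findings are thus among the better protected. This stands, and it confines the gap to AEs that newly arise in the short screening window.

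It can also be said that a single continuing record is an inference. The sentence in 12.3 on events that become serious follows a reporting deadline and does not mention onset dates. The AE reporting figure (Figure 12-1) and the CRF instructions are not available here. This stands in part. For conversion to serious, 12.2 and 12.3 both treat the change as belonging to the existing event, and nothing assigns a new onset. For severity, 8.5.1 leaves the matter open.

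Finally, nothing disappears from the report. The events are listed, serious ones go through SAE reporting and the sponsor's safety committee conducts ongoing surveillance, and TEAEs are summarised without testing. This also stands and limits the consequence, but a listing entry does not correct a count in a serious-TEAE table.

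**Conclusion.** The point holds, and it is minor. An AE that first arises between the first trial-related activity and Visit 2 and becomes serious on NN-220 is excluded from the TEAE summaries by the stated rules. For an increase in severity, the outcome depends on whether 8.5.1 or 12.2 and 12.3 is followed.

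The expected number affected is about 0.1 to 0.5 events in the whole trial at the Swedish rate, and up to about 3 at the assumed rate of 4 per year. Both ranges rest on the assumed 5% to 20% worsening and on every child using the full 4 weeks of screening. No test or sample size is affected.

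Two stronger readings are not supported. A reader might infer that any problem beginning before Visit 2 and worsening on drug is lost. It is not, because worsening of conditions present at Visit 1 or found at screening must be reported as an AE. A reader might also infer that severity reached in the extension leaks into the 104-week tables. That would depend on forms being updated before the first database lock. It would concern events already counted as TEAEs, and the documents do not show whether dated grades exist to tell.

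**What to change.** In SAP 2.4.2 and 2.4.3, and in Protocol 17.4.2 and 17.4.3, define a TEAE as an event whose onset is on or after the treatment start date used in that section, or whose onset is earlier but which increases in severity or becomes serious on or after that date, within the same closing window.

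State that each such worsening is counted once: either through the original record, using dated follow-up forms, or through a new record with the date of worsening as its onset. Doing both would count one worsening twice in the number of events and the event rate. Reconcile 8.5.1 with 12.2 and 12.3 so that sites follow the route chosen.

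The cost is a short addition to each definition, an AE recording instruction, and a check of the few records with onset before Visit 2. The SAP follows protocol version 2.0 of 3 March 2016, after the planned last first visit of 26 December 2014, so new forms for screening AEs would probably be retrospective. Using the original record avoids that if its follow-up forms show when the change occurred, which should be confirmed first. The downside is a slightly higher TEAE count.
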